Note: Patients on thyroid replacement therapy can be included if the dosage of thyroxin has been stable for at least 3 months prior to screening and the patient's sensitive thyroid stimulating hormone (s-TSH) levels are within $\pm 10\%$ of the normal range of the laboratory at the screening visit.

E 28. Laboratory findings during the screening period (not including randomization labs, except for pregnancy test):

- A) Serum TG >400 mg/dL (4.52 mmol/L) (1 repeat lab is allowed)
- B) Positive serum or urine pregnancy test in women of childbearing potential
- C) Positive test for Hepatitis B surface antigen or Hepatitis C antibody
- D) eGFR <15 mL/min/1.73 m² according to 4-variable modification in diet of renal disease (MDRD) equation
- E) ALT or AST $>3 \times$ ULN (1 repeat lab is allowed)
- F) Creatine Phosphokinase (CPK) $>3 \times$ ULN (1 repeat lab is allowed)

E 29. Conditions/situations such as:

- Patients with short life expectancy
- Requirement for concomitant treatment that could bias primary evaluation
- Impossibility to meet specific protocol requirements (eg, need for hospitalization, ability to make study visits, etc)
- Patient is the Investigator or any Sub-Investigator, research assistant, pharmacist, study coordinator, other staff or relative thereof directly involved in the conduct of the protocol
- Uncooperative or any condition that could make the patient potentially non-compliant to the study procedures

- Any technical/administrative reason that makes it impossible to randomize the patient in the study
- Any clinically significant abnormality identified at the time of screening that in the judgment of the Investigator or Sub-Investigator would preclude safe completion of the study or constrain endpoint assessments such as major systemic diseases, patients with short life expectancy

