9 ASSESSMENT OF INVESTIGATIONAL MEDICINAL PRODUCT

Lipid parameters

Blood sampling to determine lipid parameters (ie, TC, LDL-C, HDL-C, TG, non-HDL-C, Apo B, Apo A-1, ratio Apo B/Apo A-1, Apo C III, LDL particle size and number, and Lp [a]) should be performed in the morning, in fasting condition (at least 10 to 12 hours fast and refrain from smoking). Alcohol consumption within 48 hours and intense physical exercise within 24 hours preceding the blood sampling are discouraged.

TC, HDL-C, TG, Apo B, Apo A-1, Apo C-III and Lp(a) will be directly measured by the Central Laboratory as per the schedule in [Section 1.2](#). LDL-C will be directly measured via beta quantification method by the Central Laboratory as per the schedule in Section 1.2. LDL-C will be calculated using the Friedewald formula at all visits (except Weeks 4 and 32). If TG values exceed 400 mg/dL (4.52 mmol/L) then the central lab will reflexively measure (via the beta quantification method) the LDL-C rather than calculating it. Non-HDL-C will be calculated by subtracting HDL-C from the TC. Ratio Apo B/Apo A-1 will be calculated. Triglyceride rich lipoprotein will be calculated by total cholesterol minus HDL cholesterol minus LDL cholesterol. Detailed procedures of sample preparation, storage and shipment will be described in the specific laboratory manual which will be provided to sites.

All patients will qualify for randomization based on the LDL-C value obtained at Week -3 visit. If the patient is not fasting at this or any other visit requiring fasting, then he/she will be asked to come the day after or as close as possible to this date for the blood sampling.

Communication of lipid results by central lab

The lipid results from blood samples obtained after the randomization visit will not be communicated to the Investigators. However, sites will be notified in the event of a TG level ≥ 500 mg/dL (5.65 mmol/L) obtained any time after randomization (ie, TG alert). Repeat testing should be done as soon as possible after a TG alert. For a confirmed TG alert, please refer to relevant information in [Section 8.8.1](#).

Efficacy endpoints will not be considered as AEs, such as those involving abnormalities in lipid levels, unless meeting the criteria in [Section 10.4](#).

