10 STUDY PROCEDURES

The window period for Week 0 is +3 days. The window period for Weeks 8, 12 and 24 is ± 3 days. The window period for Weeks 4, 20, and 32 is ± 7 days.

For all visits after Day 1/inclusion visit, if one visit date is changed, then the next visit should take place according to the original schedule as outlined in the Study Flow Chart ([Section 1.2](#)).

Blood sampling

All blood sampling, including the blood sampling for determination of lipid parameters (eg, TC, LDL-C, HDL-C, TG, non-HDL-C, Apo A, Apo B, Apo C-III, Lp(a), LDL particle size and number) and also for plasma glucose should be performed in the morning, in fasting condition (ie, overnight, at least 10 to 12 hours fast and refrain from smoking), and before IMP injection for all site visits throughout the study. Alcohol consumption within 48 hours and intense physical exercise within 24 hours preceding the blood sampling are discouraged.

Note: if the patient is not in fasting conditions, the blood sample will not be collected and a new appointment will be given to the patient for the day after (or as close as possible to this date), with instructions to fast (see above conditions).

Laboratory tests

The laboratory data are collected in accordance with the study schedule and the details provided in the Study Flow Chart ([Section 1.2](#)).

- Hematology: all visits except Weeks 4 and 20; may be performed at Week 0 as applicable and based on the clinical discretion of the Investigator
- Chemistry: all visits except Visits 3 and 6; may be performed at Week 0 as applicable and based on the clinical discretion of the Investigator, except for plasma glucose which should be performed at Week 0 for all patients
- HbA1c: screening and Weeks 0, 12, and 24
- Lipid panel: screening and Weeks 0, 8, 12, 20, and 24
- Measured LDL-C via beta quantification: Weeks 0, 12, and 24
- Other lipid assessments (Apo B, Apo A-1, Apo C-III, LDL particle size and number, Lp[a]): Weeks 0, 12, and 24
- Liver panel: all visits except Visits 3 and 6; may be performed at Week 0 as applicable and based on the clinical discretion of the Investigator. In case of total bilirubin values above the normal range, differentiation into conjugated and non-conjugated bilirubin will occur automatically
- Creatine Phosphokinase (CPK): all visits except Visits 3 and 6; may be performed at Week 0 as applicable and based on the clinical discretion of the Investigator.

- Hepatitis B surface antigen: screening only.

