 - Chemistry: plasma glucose, sodium, potassium, chloride, bicarbonate, calcium, phosphorous, urea nitrogen, creatinine, uric acid, total protein, albumin, LDH, and γGT
 - HbA1c
 - Liver panel (ALT, AST, ALP, and total bilirubin)
 - CPK
 - Hepatitis B surface antigen and Hepatitis C antibody tests.
 - Serum pregnancy test (women of childbearing potential only).

- TSH (for patients on thyroid hormone replacement therapy)
- C-peptide

Note: if the patient is not in fasting conditions, the blood sample will not be collected and a new appointment will be given the day after (or as close as possible to this date) to the patient with instruction to be fasted (at least 10 to 12 hours fasting). Alcohol consumption within 48 hours and intense physical exercise within 24 hours preceding the blood sampling are discouraged.

- Perform injection training

Injection training should be provided as outlined in [Section 8.1](#). The training injection (placebo) should be administered by the patient or another designated person (such as spouse, relative, etc) at the study site under supervision of site staff with appropriate feedback.

- If patient will undergo the second optional injection training, then the following steps are needed. However, if patient does not need a second optional training injection with placebo then do not perform these steps.
 - Recontact IVRS/IWRS for allocation of a second new packaging number for a second training kit.
 - Record the second packaging number allocated in e-CRF.
 - Dispense the second training injection kit to the patient for self-administration.

Note: All patients will be qualified for randomization based on the LDL-C value obtained at this visit.

- Give an appointment for the next visit.
- If it is planned to have another designated person administer the injections to the patient during the study, and the designated person did not perform injection training at the screening visit, then the designated person should also be present at the next visit (Week 0).
- Dispense the Insulin log and instruct the patient on how to complete it.

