2 STATISTICAL AND ANALYTICAL PROCEDURES

2.1 ANALYSIS ENDPOINTS

The baseline value is defined as the last available value obtained prior to the first double-blind investigational medicinal product (IMP) injection, including values obtained at the day of randomization since all blood samples for laboratory assessment taken on this day are performed prior to the first IMP injection. For patients randomized and not treated, the baseline value is defined as the last available value obtained up to the date and time of randomization.

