2.4.5.1 Analysis of primary efficacy endpoint(s)

2.4.5.1.1 Primary efficacy analysis

Separate analyses will be performed for Type 1 diabetes patients on one hand (alpha risk = 0.05) and Type 2 diabetes patients on the other hand (alpha risk = 0.05), as well as in the pool population (alpha risk = 0.05). All outputs described below will be first described separately on the Type 1 diabetes patients and on the Type 2 diabetes patients, and then on the pooled data.

The percent change in calculated LDL-C from baseline to Week 24 as defined in [Section 2.1.3.1](#) will be analyzed in the ITT population using a mixed effect model with repeated measures (MMRM) approach. All post-baseline data available within Week 8 to Week 24 analysis windows will be used and missing data are accounted for by the MMRM model. The model for assessing the treatment effect in the pooled data will include the fixed categorical effects of treatment group (alirocumab versus placebo), randomization strata (ie, diabetes type, as per IVRS), time point (Week 8, Week 12, Week 20 and Week 24), treatment group-by-time point interaction, and strata-

by time point interaction, as well as the continuous fixed covariates of baseline calculated LDL-C value and baseline value-by-time point interaction. The model for assessing the treatment effect by diabetes type will include an additional interaction term: the treatment group-by-strata-by-time point interaction. The significance level (P-value) of the treatment group-by-strata interaction term at Week 24 will be also provided for this model for descriptive purpose. In case of non-convergence of the model, a model with less interaction terms will be fit.

These models will be run using SAS® Mixed procedure with an unstructured correlation matrix to model the within-patient errors. Parameters will be estimated using restricted maximum likelihood method with the Newton-Raphson algorithm. Denominator degrees of freedom will be estimated using Satterthwaite's approximation. This model will provide baseline adjusted LS means estimates at Week 24 for both treatment groups with their corresponding standard errors (SEs). To compare the alirocumab group to the placebo group, an appropriate contrast statement will be used to test the differences of these estimates, at the 2-sided 0.05 level. LS-mean difference versus placebo and the corresponding 95% confidence intervals (CIs) will be provided. Forest plot will also be provided.

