2.4.5.2 Analyses of secondary lipid efficacy endpoints

2.4.5.2.1 Continuous endpoints anticipated to have a normal distribution

Continuous secondary variables defined in [Section 2.1.3.2](#) anticipated to have a normal distribution (eg, lipids other than TG, TGRL and Lp(a)) will be analyzed using the same MMRM model as for the primary endpoint. Specifically, the model for assessing the treatment effect in the pooled data will contain fixed categorical effects of treatment group, randomization strata (as per IVRS), planned time points to Week 24, treatment group-by-time point interaction, and strata-by-time point interaction, as well as, the continuous fixed covariates of corresponding baseline value and baseline value-by-time point interaction. The significance level (P-value) of the treatment-by-strata interaction term at Week 24 will be also provided for this model for descriptive purpose. In case of non-convergence of the model, a model with less interaction coefficients will be fitted. A forest plot will be provided for percent change in calculated LDL-C from baseline to week 24 on mITT population.

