2.4.5.2.2 Continuous endpoints anticipated to have a non-normal distribution

Continuous secondary efficacy endpoints defined in [Section 2.1.3.2](#), anticipated to have a non-normal distribution (eg, TG, TGRL and Lp(a)), will be analyzed using a robust regression model (ie, ROBUSTREG SAS procedure with M-estimation option) with treatment group as main effect, and randomization strata (as per IVRS) and corresponding baseline value(s) as covariate. The model for assessing the treatment effect by diabetes type will also include the treatment group-by-strata interaction. In case of non-convergence of the model, a model with less interaction coefficients will be fit. Missing values will be addressed using a multiple imputation model (see [Section 2.4.5.1.3](#)) that will at least include the same variables as used in the robust regression model (7). In the robust regression model, the analyzed endpoint at time point of interest will be derived from observed and imputed lipid values at this time point. The treatment group combined means will be provided with respective SE estimates. The combined mean difference between the treatment groups will be provided with the SE, 95% CI and p-value through the SAS MIANALYZE procedure. The analysis will be performed by diabetes type and on the pooled data.

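### The lipid models adjust for one pre-dose value although two are scheduled; adding the Week -3 value would give a modest, nearly free gain in precision, mainly for HDL-C, TG and the Type 1 stratum

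*SAP*

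**What the plan says.** SAP 2.1: "The baseline value is defined as the last available value obtained prior to the first double-blind investigational medicinal product (IMP) injection". In the normal course this is the Week 0 sample.

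SAP 2.4.5.1.1 gives the primary MMRM treatment, diabetes type, time point and their interactions, "as well as the continuous fixed covariates of baseline calculated LDL-C value and baseline value-by-time point interaction". SAP 2.4.5.2.1 uses "the continuous fixed covariates of corresponding baseline value and baseline value-by-time point interaction" for the normally distributed secondary endpoints. SAP 2.4.5.2.2 fits the robust regression for TG "with treatment group as main effect, and randomization strata (as per IVRS) and corresponding baseline value(s) as covariate". The imputation model in SAP 2.4.5.1.3 takes the baseline value and the values at Weeks 8, 12, 20 and 24.

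Protocol 10 schedules a second pre-dose panel: "Lipid panel: screening and Weeks 0, 8, 12, 20, and 24". It contains TC, calculated LDL-C, HDL-C, TG and non-HDL-C. Its stated use is eligibility; Protocol 10.1.1 notes: "All patients will be qualified for randomization based on the LDL-C value obtained at this visit". Measured LDL-C, Apo B, Lp(a) and LDL particle number and size are sampled only at Weeks 0, 12 and 24.

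**The concern.** One lipid value is a noisy reading of a patient's usual level. Its noise enters the percent change through the denominator, and adjusting for the same value removes only part of it. A second pre-randomization reading of the same analyte, taken 8 to 21 days before Day 1, carries information on the usual level that the Week 0 value lacks. The plan collects it and then does not use it in any model.

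At stake is interval width, and with it some power where effects are small. The protocol's introduction describes the earlier TG and HDL-C effects as modest and gives no figures. In the fixed sequence of SAP 2.4.5.3, a miss on HDL-C blocks formal claims on TG and on LDL particle number and size; a miss on TG blocks the last two. Each diabetes type is also analysed at its own 0.05 level, and Type 1 is capped at about 100 patients (about 67:33) and may close short. Precision there has to come from data already in hand.

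**Working it through.** **Inputs from the documents.** Two-sided 0.05; 2:1 allocation; about 400 Type 2 (267:133) and up to 100 Type 1 (67:33) patients. Earlier LDL-C change was -45.6 to -48.9% on alirocumab with up-titration and +0.5 to +4.2% on placebo, so the smallest difference is 45.6 + 0.5 = 46.1 points. The sample-size text is redacted, so no SD, power or correlation can be reproduced.

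**Assumptions.** r is the correlation of Week -3 with Week 0. q is the correlation of either pre-dose value with Week 24.

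**Formula.** Adjusting for Week 0 alone leaves residual variance 1 - q². Adjusting for both leaves 1 - 2q²/(1 + r). The relative gain is

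q²(1 - r) / [(1 + r)(1 - q²)],

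which becomes ρ²/(1 + ρ)² when r = q = ρ. With complete data, this ANCOVA result is also the MMRM's Week 24 contrast.

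| r | q | Gain |
|---|---|---|
| 0.3 | 0.3 | 5.3% |
| 0.5 | 0.5 | 11.1% |
| 0.7 | 0.7 | 17.0% |
| 0.8 | 0.8 | 19.8% |
| 0.7 | 0.5 | 5.9% |
| 0.8 | 0.6 | 6.2% |
| 0.9 | 0.7 | 5.1% |
| 0.9 | 0.5 | 1.8% |

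For example, r = 0.7 and q = 0.5 give 0.25 × 0.3 / (1.7 × 0.75) = 0.059.

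**Simulation of the actual endpoint.** Percent change is not linear in baseline, so ANCOVA on percent change was simulated with log-normal lipids and 2:1 allocation.

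- Calculated LDL-C (median 105 mg/dL, coefficient of variation 30 to 40%, Week -3 value at least 70 mg/dL, effect -47%, between-patient response SD 0 to 25 points): the variance of the treatment difference falls by about 1 to 14.5%.
- HDL-C (effect +5%, coefficient of variation 30%): about 4 to 17%.
- TG (effect -8%, coefficient of variation 50%): about 3 to 10%. This used ordinary ANCOVA, not the planned imputation with M-estimation.

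**What a gain is worth.** A gain v narrows the interval by 1 - √(1 - v) and is worth N/(1 - v) - N patients.

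| v | Narrower interval | Patients on 400 | 80% power becomes |
|---|---|---|---|
| 5% | 2.5% | 21 | 82% |
| 10% | 5.1% | 44 | 84% |

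**Primary endpoint.** In Type 2, power for 46.1 points is about 100% at any SD from 25 to 60. In Type 1 at SD 60, the standard error is 60 × √(1/67 + 1/33) = 12.76, the ratio is 46.1/12.76 = 3.61, and power is Φ(3.61 - 1.96), about 95%. A 15% gain raises the ratio to 3.61/√0.85 = 3.92 and power to about 97.5%. At SD 50 power is 99.1% without any gain, and at SD 40 it is 99.97%. The SDs in the LDL-C simulation stayed below 40.

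**Reach.** Ten of the 16 key secondary endpoints have a Week -3 value of the same analyte. Six do not: measured LDL-C at Weeks 12 and 24, Apo B, Lp(a), and LDL particle number and size.

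**The case against.** The strongest reply is that nothing here is wrong. Adjustment for the last pre-dose value is unbiased and keeps the type I error. That stands: this is an efficiency point.

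A reader might infer a gain of 5 to 20% for all the panel lipids. That range needs r = q, with correlations from 0.3 to 0.8. A patient model with constant level and independent noise forces this equality: for HDL-C with assumed log SDs of 0.25 between and 0.10 within patients, ρ = 0.0625/0.0725 = 0.86 and the log-scale gain is about 21%. If the correlation with Week 24 is 0.76 or 0.70 instead, the gain falls to about 10% or 7%. The documents supply nothing that would support the upper figures.

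The plural in the wording for TG could be read as allowing more than one baseline value. SAP 2.1 defines a single one, however, with Week -3 only as the fallback when no later pre-dose value exists. For TG, the omission is therefore an inference, though the natural one.

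The practical objections also stand. Screening TG may be repeated once, so more than one screening value can exist. Calculated LDL-C is not produced when TG exceeds 400 mg/dL, and SAP 2.1.3 bars the reflex measured value from calculated LDL-C endpoints. Membership of the ITT population does not require a Week -3 value, so a missing covariate would drop patients from the MMRM. These call for a short handling rule; they do not remove the gain.

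**Conclusion.** The point holds as an optional improvement of modest size. The primary MMRM and the models for non-HDL-C, TC, HDL-C and TG leave out a scheduled pre-randomization value of the same analyte. Under the assumptions shown, using it would cut the variance of the treatment difference by roughly 1 to 15% for calculated LDL-C and 3 to 17% for HDL-C and TG; the low end applies if r exceeds q.

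Two further readings go too far. The first is that the primary analysis is at risk: its test is practically unaffected, and only its interval narrows slightly. The second is that all key secondary analyses lose precision: six have no Week -3 sample, and HDL-C and TG come late in the order, with only two endpoints after TG. The useful gain is for those two endpoints and for Type 1 diabetes.

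**What to change.** Before unblinding, and listed in SAP 1.5, where added model terms are already recorded:

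- Add the Week -3 value of the same analyte and its time-point interaction to the MMRMs for calculated LDL-C, non-HDL-C, TC and HDL-C.
- Add Week -3 fasting TG to the TG robust regression and its imputation model.
- Add Week -3 calculated LDL-C to the LDL-C imputation model and to the sensitivity ANCOVAs, so that they match the primary model.
- Use the last valid screening value taken before the baseline sample. Fill a missing one by a single imputation blind to treatment (the overall mean, or the patient's own baseline value), so that no ITT patient is dropped.
- Leave the endpoint and baseline definitions unchanged.

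The cost is SAP wording, one extra covariate per visit and the handling rule. No new data are needed.

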2.4.5.1.2 Model assumption checks

The following analyses will be performed by diabetes type and in the pooled data.

Homogeneity of treatment effect across baseline calculated LDL-C levels:

In order to check the homogeneity of treatment effect versus baseline calculated LDL-C, the following interaction terms will be added in the primary MMRM model:

- Treatment group * baseline calculated LDL-C
- Treatment group * time-point * baseline calculated LDL-C

Within the framework of this model with interaction terms, a graph presenting the LS means difference versus placebo at Week 24 and the corresponding 95% CI will be provided by baseline calculated LDL-C value.

Analysis of residuals:

The analysis of the residuals of the MMRM will be primarily based on studentized residuals. It will include:

- Normality of studentized residuals, presented graphically using histogram and quantile quantile (QQ)-plot;
- Plot of studentized residuals versus predicted values;

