1 OVERVIEW AND INVESTIGATIONAL PLAN

1.1 STUDY DESIGN AND RANDOMIZATION

This is a Phase 3b, multinational, multicenter, randomized, double-blind, placebo-controlled, parallel group, unbalanced (2:1 ratio) and stratified study.

After a screening phase of up to three weeks, patients will be centrally randomized via interactive voice response system (IVRS) or interactive web response system (IWRS) to one of the two treatment groups (alirocumab:placebo) and will be treated in a double-blind manner for approximately 24 weeks. Randomization ratio will be 2:1 (alirocumab:placebo) and patients will be stratified by diabetes type (ie, Type 1 diabetes versus Type 2 diabetes).

Approximately 500 patients will be randomized (333 in the alirocumab group and 167 in the placebo group). The recruitment of patients with Type 2 diabetes will complete when approximately 400 patients have been randomized. Recruitment of patients with Type 1 diabetes will continue until approximately 100 patients have been randomized or the end of the targeted recruitment period (summer 2016), whichever comes first.

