2.1.3.1 Primary efficacy endpoint(s)

The primary efficacy endpoint is the percent change in calculated LDL-C from baseline to Week 24 in the intent-to-treat (ITT) population. Primary endpoint is defined as: $100 \times (\text{calculated LDL-C value at Week 24} - \text{calculated LDL-C value at baseline}) / \text{calculated LDL-C value at baseline}$.

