2.4.5.1.4 Subgroup analyses

To assess the homogeneity of the treatment effect across various subgroups, treatment-by-subgroup factor, time point-by-subgroup factor and treatment-by time point-by subgroup factor interaction terms and a subgroup factor term will be added as fixed factors in the primary MMRM model for the pooled data described in [Section 2.4.5.1.1](#). For assessing the treatment effect by diabetes type, the same model will be fitted within each stratum, therefore without the strata factor and the interactions of strata with other factors. In case of non-convergence of the model, a model with less interaction coefficients will be fitted.

As for the primary efficacy analysis, all outputs will be first described separately on the Type 1 diabetes patients and on the Type 2 diabetes patients, and then on the pooled patients population.

LS means difference versus placebo at Week 24 will be provided, as well as the corresponding standard error (SE) and 95% CI, within each subgroup. The significance level of the treatment-by-subgroup factor interaction term at Week 24 will be also provided for each factor for descriptive purpose. Forest plots will be provided. For each subgroup analysis, subgroups will be included in

the analysis only if there are ≥ 10 patients by subgroup and treatment arm. Otherwise, unless specified below, the subgroups not meeting the required number of patients will be pooled to form larger subgroups if possible, or they will be excluded from analysis.

Subgroups of interest are:

- BMI: <25 , [25-30[, ≥ 30 kg/m²;
- Gender: Female, Male;
- Menopausal status, for female only: Yes, No;
 1. For post-menopausal women: type of hormone replacement therapy : estrogen only, estrogen and progesterone, no estrogen or progesterone;
- Race: White/Caucasian, non-White/Caucasian;
- Ethnicity: Hispanic, non-Hispanic, Not Reported/Unknown;
- Region: North America, Europe;
- Age: <65 , [65–75], >75 / <65 , ≥ 65 years old;
- Duration of diabetes : <5 , [5-10], >10 years if the number of patients by subgroup meets the requirement (see above); otherwise by tertiles;
- ASCVD as per protocol: Yes, No;
- ASCVD including TIA as per the 2013 AHA/ACC guideline (see [Section 2.1.1](#)): Yes, No;
- Background LMT:
 2. Any statin versus no statin at randomization
 3. no LMT (neither statin or other LMT), versus other LMT only (without statin), versus statin alone, versus any statin plus other LMT

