 4. High intensity statin at randomization vs medium or low intensity statin at randomization
- Prior history of myocardial infarction (Silent or acute MI) or ischemic stroke: Yes, No;
- CKD: Yes, No (from cardiovascular medical history CRF page);
- Estimated GFR class: <30 , [30- 60[, [60-90[, ≥ 90 mL/min/1.73 m². If there are not enough patients with eGFR <30 , the <30 and the [30-60[categories will be pooled together;
- Baseline albumin/creatinine ratio: <30 , [30-300[, ≥ 300 mg/g (<3.39 , [3.39-33.9[, ≥ 33.9 mg/mmol);
- Diabetic kidney disease category as defined below ([Appendix C](#)) (1):
 1. Category 1 : G1A1, G2A1
 2. Category 2 : G1A2, G2A2, G3aA1
 3. Category 3 : G1A3, G2A3, G3aA2, G3bA1
 4. Category 4 : G3aA3, G3bA2, G3bA3, G4A1, G4A2
 5. Category 5 : G4A3, G5A1, G5A2, G5A3

If the numbers of patients by subgroup don't allow this subgroup analysis, other groupings will be explored.

- Baseline calculated LDL-C: <100, [100-130[, [130-160[, ≥ 160 (<2.59[, [2.59-3.37[, [3.37-4.14[, ≥ 4.14 mmol/L) if the number of patients by subgroup meets the requirement (see above). Otherwise one of the following groupings will be explored:
 1. <100[, [100-130[, ≥ 130 (<2.59[, [2.59-3.37[, ≥ 3.37 mmol/L)
 2. by tertiles
- For this specific subgroup factor, the MMRM model will include the same covariates than for other subgroup factors, except that the baseline calculated LDL-C value will be replaced by the baseline calculated LDL-C category. Therefore, the model for the overall population will include fixed categorical effects for treatment group, randomization strata (as per IVRS), baseline calculated LDL-C category, time point, and the interactions treatment-by-time point, strata-by time point, baseline calculated LDL-C category-by-time point, treatment group-by-baseline calculated LDL-C category, and treatment group-by-baseline calculated LDL-C category-by-time point. For assessing the treatment effect by diabetes type, the same model will be fitted within each stratum, therefore without the strata factor and the interaction strata-by time point.
- Baseline non-HDL-C: <130, [130-160[, [160-190[, ≥ 190 (<3.37, [3.37-4.14[, [4.14-4.91[, ≥ 4.91 mmol/L)) if the number of patients by subgroup meets the requirement (see above). Otherwise one of the following groupings will be explored:
 1. <130[, [130-160[, ≥ 160 (<3.37, [3.37-4.14[, ≥ 4.14 mmol/L)
 2. by tertiles (only if no sufficient patients in previous grouping)
- Baseline TGRL :
 1. <30 mg/dL, ≥ 30 mg/dL

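### The baseline LDL-C homogeneity graph and subgroup use one error-prone value as both denominator and moderator, which biases them toward a weaker percent effect at high baseline

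*SAP*

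**What the plan says.** SAP 2.1.3.1 defines the response: "The primary efficacy endpoint is the percent change in calculated LDL-C from baseline to Week 24", with the baseline value as divisor. SAP 2.1 defines baseline as one value, the last available before the first double-blind injection, not an average.

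The same baseline value then serves as moderator in two places.

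- **SAP 2.4.5.1.2 (model assumption checks).** "In order to check the homogeneity of treatment effect versus baseline calculated LDL-C", treatment-by-baseline and treatment-by-time-by-baseline terms are added to the primary MMRM. The output is a graph of the Week 24 difference from placebo, with 95% CI, by baseline LDL-C. No P-value or decision rule is attached.
- **SAP 2.4.5.1.4 (subgroups).** "To assess the homogeneity of the treatment effect across various subgroups", treatment-by-subgroup terms are added. A forest plot is produced, with a Week 24 interaction P-value labelled descriptive. For baseline LDL-C the model is the usual one, "except that the baseline calculated LDL-C value will be replaced by the baseline calculated LDL-C category".

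Both analyses are run by diabetes type and on the pooled data. I found nothing in either document that addresses error in the shared baseline value.

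**The concern.** A reader will take these outputs to show whether alirocumab's percent reduction depends on how high a patient's LDL-C is. A baseline value that is high partly by chance tends to be followed by a lower value. This gives percent change a negative slope on baseline in each arm. That slope is proportional to the arm's Week 24/baseline ratio, so in the alirocumab arm it is about half the placebo slope. The lines are then not parallel even if the drug multiplies everyone's underlying LDL-C by the same factor, and the gap between arms narrows as baseline rises.

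What is at stake is the description of benefit at high LDL-C. This is bias, so a larger sample makes it more visible and does not remove it.

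**Working it through.** **The plan's own figures.** "Approximately 500 patients will be randomized (333 in the alirocumab group and 167 in the placebo group": 500 × 2/3 = 333.3 and 500 × 1/3 = 166.7, so the split reproduces. At 2:1, about 400 Type 2 patients give 267:133 and about 100 Type 1 patients give 67:33. The sample-size inputs are redacted.

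**Inputs from the documents.** Protocol section 4 reports mean LDL-C changes of -45.6% to -48.9% on the up-titration regimen and +0.5% to +4.2% on placebo. I used Week 24/baseline ratios of 0.52 and 1.02. Entry depends on a separate Week -3 value of at least 70 mg/dL.

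**Assumptions, because the documents give no figures.** True LDL-C is lognormal with median 105 mg/dL and between-patient CV 30%. Within-patient CV is 5-20%. The log-SD of individual response to alirocumab is 0.2-0.4.

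**Mechanism.** Let X be observed baseline, r its reliability, m the mean and k the arm's ratio. Then approximately

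E(% change | X) = 100 × {k[r + (1 - r)m/X] - 1},

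and the treatment difference is 100 × (0.52 - 1.02) × [r + (1 - r)m/X] = -50 × [r + (1 - r)m/X].

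At within-patient CV 15%:

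- r = ln(1.09)/[ln(1.09) + ln(1.0225)] = 0.0862/0.1085 = 0.794
- m = 105 × √1.09 ≈ 110
- X = 80: -50 × (0.794 + 0.206 × 110/80) = -50 × 1.077 = -53.9 points
- X = 160: -50 × (0.794 + 0.206 × 110/160) = -50 × 0.936 = -46.8 points

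The true difference is -50 throughout. Simulation, which includes the entry cut, gave about -55 and -47.

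**How often a constant effect looks heterogeneous.** Monte Carlo, 1,500-6,000 trials per cell. Percent change was regressed on arm, baseline and their product. With complete data and all terms crossed with time, this matches the Week 24 contrast of the unstructured MMRM; the stratum terms were left out. Entries are nominal two-sided 5% rejection rates.

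| Within-patient CV | Pooled, 500 | Type 2, 400 | Type 1, 100 | Category F test, pooled |
|---|---|---|---|---|
| 5% | 2-4% | 1-4% | 2-3% | 1-2% |
| 10% | 9-29% | 7-24% | 4-10% | 3-18% |
| 15% | 35-59% | 31-48% | 9-18% | 18-39% |
| 20% | 62-79% | 54-67% | 16-25% | 37-59% |

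A further pooled run with a constant 50% reduction gave 1-2%, 14-20%, 39-52% and 69-77%. With no baseline error and robust SEs, rejection was 4.2-5.6%, so the excess comes from baseline error.

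Sensitivity at pooled N, CV 15% and response log-SD 0.4: between-patient CV of 20% gives 56%, 40% gives 22%, and additive error gives 35%. Raising the response log-SD to 0.6, at between-patient CV 30%, gives 18%.

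**With up-titration.** Reductions of 45% on 75 mg and 60% on 150 mg were assumed; about one third of patients were up-titrated. The true effect then strengthens with baseline, by -0.09 to -0.12 points per mg/dL. The mean slope from the percent-change model was about -0.05, +0.02 and +0.09 at CV 10, 15 and 20%. The real gradient shrinks, then changes sign.

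**Log scale.** With response log Y and covariate log X, a constant ratio adds log k to the intercept, and the slope is r in both arms. The lines are parallel when the percent effect is constant. Under a constant effect this model rejected 4-6% with robust SEs and 1-2% with a common variance. Under up-titration it kept the correct sign and, with robust SEs, detected the gradient in 75-96%, 53-76% and 32-51% of trials at CV 10, 15 and 20%.

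**The case against.** The strongest reply is that the percent-change check does what its section title says. The primary MMRM assumes one baseline slope common to both arms, and the added terms relax exactly that. Unequal slopes from regression to the mean are a genuine departure from the assumption and ought to be visible. Moreover, the endpoint is defined on observed baseline, which precedes randomisation, so the randomised difference at a given observed baseline is a valid conditional effect on that endpoint. It misleads only when read as the effect at a given underlying LDL-C. Both points stand. They are reasons to keep the percent-change model; they do not make it a good guide to whether the percent reduction varies with LDL-C.

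A reader might infer more than the documents support:

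- **That the plan falsely rejects homogeneity as a formal test.** SAP 2.4.5.1.2 produces only a graph with a CI, and the subgroup P-value is descriptive. The 5% level used above is a yardstick; the SAP sets none for these interactions.
- **That rejection is always far above 5%.** There is no inflation at 5% within-patient error, and at 10-15% it is modest in Type 1 (4-18%).
- **That the graph will show a weaker effect at high baseline in this trial.** Dosing depends on Week 8 LDL-C, so a constant Week 24 percent effect is not expected. At 10% error the mean fitted slope still ran the true way, though attenuated.
- **That baseline non-HDL-C is distorted equally.** This was not computed, and that subgroup model retains continuous baseline LDL-C.

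**Conclusion.** The concern holds as a bias in descriptive output. Both analyses lean toward a weaker percent effect at high baseline LDL-C. In the pooled and Type 2 data the lean is enough to suggest heterogeneity where there is none in roughly a third or more of trials at 15% within-patient error under the main assumptions; wider between-patient spread or a more variable response lowers this to about 20%. It can equally hide or reverse a real gradient.

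The direction follows from the algebra whenever baseline carries error and the arm ratios differ. The size rests on within-patient, between-patient and response variability that the documents do not give, and the up-titration results rest on assumed dose effects. The primary treatment contrast, for which "an appropriate contrast statement will be used to test the differences of these estimates, at the 2-sided 0.05 level", and the key secondary hierarchy in SAP 2.4.5.3 do not use these interactions and are unaffected.

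**What to change.** 1. **Keep** the percent-change interaction model in SAP 2.4.5.1.2 as a check of the primary MMRM's common-slope assumption. Footnote its graph, and the baseline LDL-C forest plot and P-value in 2.4.5.1.4, as affected by regression to the mean.
2. **Add** a log-scale MMRM in both places. The response is log calculated LDL-C at each visit, and the covariates are log baseline and log baseline-by-time. Use the same treatment-by-baseline (or treatment-by-category) and by-time terms, and retain continuous log baseline beside the categories. Use arm-specific residual covariance or robust SEs.
3. **State** that conclusions about homogeneity of the percent reduction across baseline LDL-C rest on the back-transformed ratio versus placebo from this model.

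Extending this to the baseline non-HDL-C subgroup is optional, since the effect there was not quantified.

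The cost is SAP wording and one additional model on data already collected. The drawback is that geometric-mean ratios will not match the arithmetic percent changes in the primary table exactly, and a footnote should say so. The primary analysis does not change.
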